#### 10.4.3 Potential Benefits of Trial Participation

By taking BCAA supplementation subjects may accelerate the recovery of cognitive symptoms after concussion injury. Successful development of this compound may modify clinical protocols for treating concussion and other types of TBI.

#### 10.4.4 Risk-Benefit Assessment

Although this study involves more than minimal risk (i.e. administration of a test substance), there is the potential for benefit directly or through new knowledge. We believe that the risk to benefit ratio is favorable and the risks are reasonable in relation to the potential benefit and new broadly applicable knowledge.

#### 10.5 Recruitment Strategy

Physicians with experience in diagnosing patients with concussion, will identify potential subjects and refer them to the study coordinator for participation in the study. These providers typically see patients within a few days of their suspected concussion. Recruitment will primarily occur through CHOP Sports Medicine, the CHOP Emergency Department, University of Pennsylvania Sports Medicine, the Hospital of University of Pennsylvania (HUP) Emergency Department, and Penn Presbyterian Medical Center Emergency Department (Presby ED).

For CHOP Sports Medicine, providers will identify potential subjects and with subject's permission, the provider will contact the study coordinator with the subject's contact information. Physicians in the CHOP Emergency Department will identify potential subjects for this study. Once a patient has been diagnosed by an ED physician with a concussion, a referral will be made to the study coordinator and a HIT-HEADS Study informational sheet will be provided to the patient. The study coordinator will arrange to complete the remainder of the screening process in a designated office or clinical exam after discharge from the ED.

For Penn Sports medicine, providers will identify potential subjects and with the subject's permission, the provider will contact the study coordinator with the subject's contact information.

Providers in the HUP ED, and Presby ED may also identify potential subjects for this study. They will provide a HIT-HEADS informational sheet to a patient once they have been diagnosed with a concussion. The patient will then contact the study coordinator if they are interested in study participation. Providers from these entities will not collect or transmit patient information to the study coordinator. Once the study coordinator has made contact with a potential subject, he or she will make arrangements with the potential subject to complete the remainder of the screening process in a designated office or clinical exam room.

Subjects may self-refer to the study. Informational flyers will also be displayed and distributed in University of Pennsylvania campus, including student gathering places, locker rooms, training facilities and sports medicine clinics to inform subjects about the study. Patients greater than 10 years of age that had a sports physical in the last year will be contacted and will receive an informational flyer, a letter from the PI, and a business card in the mail. Those patients that selected to receive CHOP emails will also receive an email from the PI.

[name], Department of Biomedical and Health Informatics (DBHi) will query the CHOP EPIC system for patients, ages 11 - 34 years, who, in the previous 24 hours, have been diagnosed with a concussion (ICD-9-CM codes 850, 850.0, 850.1, 850.10, 850.11, 850.5, 850.9) or made a call to the triage nurse after business hours with the complaint of a concussion . The search will be limited by those departments listed above. The report will be run daily and the results emailed to the study team. A medical record review using the EPIC database will be conducted by the study team to determine which patients are eligible for contact about the study. Specifically, the medical record will be searched for the manner and time of the concussion to determine which patients are eligible for contact. A study team member will then contact potential subjects via phone to provide information about the study.

High school administrative and athletic personnel from the school districts in the greater Philadelphia area will be given information about the study through informational fliers. Additional information about how to refer concussed players to the study will be communicated to nurses, coaches and team medical staff if the school is interested in participation. As with recruitment from other domains, potential subjects will be required to

04/06/2018 V 0.16

contact the study coordinator directly and the diagnosis of concussion will be confirmed by a physician prior to enrollment.

Upon approval from high school administrative personnel, a member of the study team will attend back to school night to distribute approved study materials including flyers and business cards. Approval will be documented in the form of a letter/email of confirmation from a high school administrator.

The UNTOLD Foundation will display the approved flyer on the organization's homepage, http://www.theuntoldfoundation.org/.

The Recruitment Enhancement Core (REC) may provide assistance with recruitment plan development and may assist in identifying and contacting potential participants using the CRU, the CHOP Recruitment Registry, social media and internal communication resources. The REC also may engage community partners and facilitate outreach on behalf of the Research Institute and this CHOP research study.

## **10.6 Informed Consent/Assent and HIPAA Authorization**

Informed consent is an ongoing process that takes place between the investigator/study staff and study participants. The PI or their designee (physician co-investigators) will obtain informed consent for this research study. The consent process will occur in a designated office or clinical exam room at CHOP or Penn. It is the responsibility of the PI to ensure that informed consent has been properly obtained. The consent will include use of the information obtained during the clinical battery before enrollment and all data obtained after enrollment. Subjects may take any additional time needed to review the consent document, however, initiating the trial may not begin more than 72 hours after the time of injury. Adult subjects age  $\geq 18$  will sign the Informed Consent after full review and verbalized understanding of the protocol. If the subject is a <18 years old, enrollment will require both parental permission and subject assent.

## 10.7 Payment to Subjects/Families

Subjects will receive a possible total of \$100 for participation in this study. Amount received will depend on compliance with study procedures and will be offered in a graduated schema to encourage ongoing participation. Payment will be placed on a reloadable CHOP-issued card and money added throughout the study. Subjects will receive \$20 on the card at the time of visit 1. Each day that they input all required study data will add \$1, with a bonus of \$2 each time 3 days in a row are met and \$5 each time 7 days in a row are met, for a possible total of \$50 if all 21 days of data are entered completely. \$10 will be added for each in-person research visit that they attend (possible total of \$30 for 3 visits)..

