#### 5.5 Rescue Medication Administration

Subjects who experience side effects from the study medication, to a level that the subject requests medication to manage these symptoms, will be discontinued from the study.

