### 7.2 Secondary Endpoints

- Repeated measurements of neurocognitive functioning (CCAT test of attention, learning, and working memory) sampled over a period of 21 days.
- Clinical symptoms.
- Time to return to school/work, and sports participation.
- Tolerability of BCAA's based on AE's.
- Compliance.
- Safety and incidence of AE's and serious adverse events (SAE's).

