## 9 SAFETY MANAGEMENT

### 9.1 Clinical Adverse Events

Clinical AE's will be monitored throughout the study.

The study coordinator will ask the subject about the occurrence of any AE's during the scheduled study visits conducted on days 7, 14, and 22 and during unscheduled visits. A standardized question will be asked of every subject to inquire about illnesses or accidents since the previous reporting period. The study coordinator will collect complete information about AE's from subjects including:

- Descriptive text and key words of the event
- Assessment of the event severity (grade)
- Indication if the event is serious and type
- Relationship to study drug
- Start date and end date (if applicable)

The investigators, with input from the independent medical monitor, will evaluate all AE's to determine the relationship to the study drug. All recorded AE's will be followed until resolution or stabilization. An AE Log will be used to collect this information across study visits and prompt follow-up of previously reported events.

Additionally, at the final study visit, subjects will be asked to call the study coordinator and report any serious AE's that they experience following the last visit, and that they believe may be related to their treatment.

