#### 10.4.2 Risk Assessment

Risks for this study are a minor increase above minimal. Subject safety will be monitored by AE's on a weekly basis. Expected adverse experiences during this study may include gastrointestinal symptoms such as dyspepsia either from the BCAA's themselves or the 20 ounces of fluid consumed. Prior studies have shown that these symptoms when related to BCAA's are mild and transient. An informal inquiry of athletes (both male and female) from many sports indicated that drinking 20 ounces of fluid twice daily is not burdensome and within the volume typically consumed while training or competing. Should a subject report new onset gastrointestinal symptoms while on therapy, the subject will be monitored to see if these symptoms either have an alternative explanation (e.g. development of acute gastroenteritis from an identifiable source) or spontaneously resolve in less than 24 hours. The study therapy will not be held unless these symptoms persist for more than 24 hours or are severe enough to require medical attention. In this case the subject will be removed from the study and the therapy not restarted. Taking the CCAT or CDP may temporarily exacerbate concussion symptoms, which typically resolve after a short period of rest. Neurological and psychiatric symptoms induced by changes in neurotransmitters like serotonin, dopamine, norepinephrine are theoretically possible with BCAA therapy but have never been observed clinically. Emergence of any of these symptoms will result in discontinuation of the subject's participation in the study. BCAA therapy will be discontinued for any SAE related to its use.

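### Some side-effect disclosures end participation and, it appears, the subject's further earnings; Section 10.7 should state what is paid after such a removal

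*Combined protocol and SAP*

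**What the plan says.** **Payment (Section 10.7).** The section states the principle: "Amount received will depend on compliance with study procedures". Of a possible $100, $20 goes "on the card at the time of visit 1". After that, "Each day that they input all required study data will add" $1, with $2 for each run of three days and $5 for each run of seven. The stated maximum for 21 complete days is $50. Each attended visit adds $10, up to $30 for three visits. Section 5.2 gives the purpose: early recruitment showed compliance problems, so graduated rewards and progress messages were introduced.

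**Removal.**
- Section 5.5: subjects with side effects "to a level that the subject requests medication to manage these symptoms, will be discontinued from the study".
- Section 10.4.2, for gastrointestinal symptoms that last more than 24 hours or need medical attention: "In this case the subject will be removed from the study and the therapy not restarted". Emerging neurological or psychiatric symptoms also end participation.
- Section 5.6: investigators may discontinue a subject over safety concerns from any AE.
- Section 5.7: a subject who ends early is asked only to return the bottles.

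**Safety data.** Section 9.1: "The study coordinator will ask the subject about the occurrence of any AE's", at the scheduled visits and any unscheduled ones. Section 7.2 lists "Tolerability of BCAA's based on AE's" as a secondary endpoint, along with AE and SAE incidence. Section 7.3.4 summarizes AE incidence by dose and placebo.

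**The concern.** Payment accrues only by taking part, and certain disclosures end participation. A subject with one of the removal-triggering symptoms who says so would stop earning; one who says nothing would not. Staff learn of these events largely from the subject, so the scheme gives some reason to withhold the information that the tolerability and safety endpoints need.

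The sums cannot be dismissed as too small to influence anyone, because Section 5.2 relies on the same payments to change behaviour, in subjects as young as 11.

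Two things are at stake. One is completeness of AE counts in small groups: 72 subjects over five groups is about 14 each (72/5 = 14.4), so one undisclosed event moves a group's incidence by about 7 percentage points (1/14.4 = 6.9%). The other is efficacy data. Under Sections 4.3.2 and 7.4 a subject removed before Day 10 is not evaluable, so data are lost for a reason that may be related to treatment.

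**Working it through.** **1. Reproduce the plan's own total.** For *d* complete days, daily earnings are

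D(*d*) = 1×*d* + 2×floor(*d*/3) + 5×floor(*d*/7)

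D(21) = 21 + 14 + 15 = $50, as stated. The total is 20 + 50 + 30 = $100, as stated. Counting overlapping runs would give 21 + 2×19 + 5×15 = $134, so the bonuses must be for non-overlapping blocks.

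**2. Amount forgone on removal.** With *v* paid visits after Visit 1,

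forgone = 100 − [20 + D(*d*) + 10*v*]

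Assumptions: every day so far is complete, the three $10 visits are Visits 2, 3 and 4, the visit at which the disclosure is made is paid, and payment stops at removal. Visit windows are from the Schedule of Study Procedures and Section 5.2; Section 9.1 gives Days 7, 14 and 22.

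| Point of removal | Earned | Forgone |
|---|---|---|
| No complete day | 20 | $80 |
| 1 day | 20 + 1 = 21 | $79 |
| 3 days | 20 + 3 + 2 = 25 | $75 |
| Visit 2, Day 5 | 20 + 5 + 2 + 10 = 37 | $63 |
| Visit 2, Day 7 | 20 + 7 + 4 + 5 + 10 = 46 | $54 |
| Visit 2, Day 9 | 20 + 9 + 6 + 5 + 10 = 50 | $50 |
| Visit 3, Day 12 | 20 + 12 + 8 + 5 + 20 = 65 | $35 |
| Visit 3, Day 14 | 20 + 14 + 8 + 10 + 20 = 72 | $28 |
| Visit 3, Day 16 | 20 + 16 + 10 + 10 + 20 = 76 | $24 |
| Visit 4, all 21 days complete | 20 + 50 + 30 = 100 | $0 |

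If returning the bottles in person counted as a paid visit, each loss before Visit 4 would be $10 lower: $40 to $53 at Visit 2 and $14 to $25 at Visit 3. A subject who would have missed later days anyway also has less to lose than the table shows.

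**3. Which disclosures carry the penalty.**

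| Disclosure | Consequence in the plan |
|---|---|
| Asks for medication for a side effect (5.5) | Leaves the study |
| GI symptoms over 24 hours or needing medical attention (10.4.2) | Leaves the study |
| Emerging neurological or psychiatric symptoms (10.4.2) | Leaves the study |
| Any other AE with a safety concern (5.6) | May leave, investigators decide |
| Brief GI symptoms not needing medical attention (10.4.2) | Drink continues |
| SAE related to BCAA (10.4.2) | Therapy is discontinued; leaving the study is not mentioned |

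The last row matters for the fix. Within one section, a related SAE leads to stopping therapy, while persistent GI symptoms lead to leaving the study. The plan does not say whether these are meant to differ, or what either means for payment and later data.

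**The case against.** **Forfeiture is not stated.** It is inferred from pay-per-entry and pay-per-visit terms and from the silence of 5.7 and 10.7. The consent form is not among the documents read and may already protect payment. This stands as a limit; if it does, the protocol need only match it.

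**The scheme has a good reason.** It answers a documented compliance problem, holds nothing back for completion, and minors enrol with parental permission. This is fair, and the point does not call for abandoning the rewards.

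**Stronger readings are tempting but not supported.**
- A reader might take nearly $80 as the usual loss. That needs removal in the first day or so, before any scheduled AE question.
- A reader might infer that every AE report costs money. Brief GI symptoms that need no medical attention do not lead to removal under 10.4.2, and disclosure at Visit 4 costs nothing. The Visit 4 question, however, covers only the time since the previous enquiry.
- A reader might infer that silent subjects are paid to keep drinking. Payment is for entering data; Appendix 4 accepts zero bottles, so a subject can stop drinking, record it truthfully and go on earning.
- A reader might infer a known bias in the dose-placebo AE comparison. The documents give no rate of non-disclosure. Equal silence among affected subjects in all groups would shrink the absolute difference but leave the ratio unchanged, and the planned AE summary is descriptive.

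The daily forms do record nausea, drowsiness and fatigue, but as concussion symptoms; they are not named as an AE source.

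**Conclusion.** The point holds as an incentive, not as a demonstrated bias. On the plan's own figures, a disclosure that leads to removal would forgo $50 to $63 at Visit 2 and $24 to $35 at Visit 3, with a ceiling near $80 and nothing at Visit 4. At Visit 2 that is at least half of the total and at least as much as the subject has earned so far. This rests on complete entries, paid visits, and payment ending at removal. How many subjects would stay silent is unknown, and only the disclosures that lead to removal are affected. The change is worth making because it is inexpensive, removes a disincentive to safety reporting, and could keep data that would otherwise be lost before Day 10.

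**What to change.** 1. In Section 10.7 and at consent, state that a subject who stops the drink because of a side effect does not forfeit the remaining payment schedule. Such a subject may, if willing and if the investigator agrees, continue the daily forms and visits, with those data flagged as off the drink.
2. Reconcile Sections 5.5, 5.6, 5.7 and 10.4.2 with this, so that it is clear where the plan means stopping the drink and where it means leaving the study. Which clinical rule applies in each case is for the sponsor to decide.
3. In Sections 4.3.2, 7.3.2 and 7.4, say how off-drink data count toward the Day 10 evaluable set and the primary analysis.

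The cost is amendment and consent wording, and payments of up to the $100 already promised for some subjects who are off the drink. No new staff or procedures are needed. The one analytic decision it forces is item 3.

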## 10.7.1 Reimbursement for travel, parking and meals

Subjects who park at a CHOP facility that requires paid parking for any of their 4 research visits will receive parking vouchers.

## **11 PUBLICATION**

The principal investigator and co-investigators will prepare the data for publication.

## **13 APPENDICES**

#### 13.1 APPENDIX 1: Clinical Symptom Checklist

Here is a list of symptoms that people often feel when they have a concussion. For each symptom, please select the number that best describes **how long you experienced each symptom in the past day [insert date]**.

	Symptom Duration	Never experienced this symptom	Very Bi	Sometimes Today (about Very Briefly half the day long)			All Day Long	
1.	Headache	D ° 0	□ ₁ 1	□ ₂ 2	□ ₃ 3	□₄ 4	□ ₅ 5	□ ₀ 6
2.	Nausea	□ ₀ 0	□ ₁ 1	□ ₂ 2	□ ₃ 3	□₄ 4	□ ₅ 5	🗖 6 🙍
3.	Balance problems	□ ₀ 0	🗖 1 👖	□ ₂ 2	□ ₃ 3	□₄ 4	□ ₅ 5	🗖 6 👲
4.	Sleeping more than usual	D ° 0	□ ₁ 1	□ ₂ 2	□ ₃ 3	□₄ 4	□ ₅ 5	🗖 6 👲
5.	Drowsiness	D ° 0	🗖 1 👖	□ ₂ 2	□ ₃ 3	□₄ 4	□ ₅ 5	🗖 e 👲
6.	Fatigue	D ° 0	🗖 1 👖	□ ₂ 2	□ ₃ 3	□₄ 4	□ ₅ 5	🗖 6 👲
7.	Feeling "slowed down"	□ ₀ 0	🗖 1 👖	□ ₂ 2	□ ₃ 3	□₄ 4	□ ₅ 5	🗖 6 👲
8.	Feeling like "in a fog"	□ ₀ 0	🗖 1 👖	□ ₂ 2	□ ₃ 3	□₄ 4	□ ₅ 5	🗖 6 👲
9.	Difficulty concentrating	D ° 0	□ ₁ 1	□ ₂ 2	□ ₃ 3	□₄ 4	□ ₅ 5	□ ₀ 6

Here is a list of symptoms that people often feel when they have a concussion. For each symptom, please select the number that best describes **how severe the symptom has felt in the past day [insert date]**.

Symptom Severity	Not experiencing this symptom	Mild		Moderate		Severe	
10. Headache	D ° 0	□ ₁ 1	□ ₂ 2	□ ₃ 3	□ ₄ 4	□ ₅ 5	🗖 e 🧕
11. Nausea	🗖 。 🧕	□₁ 1	□ ₂ 2	□ ₃ 3	□ ₄ 4	□ ₅ 5	🗖 e 👲
12. Balance problems	🗖 。 🧕	□₁ 1	□ ₂ 2	□ ₃ 3	□₄ 4	□ ₅ 5	🗖 e 👲
13. Sleeping more than usual	🗖 。 🧕	□₁ 1	□ ₂ 2	□ ₃ 3	□₄ 4	□ ₅ 5	🗖 e 👲
14. Drowsiness	🗖 。 🧕	□₁ 1	□ ₂ 2	□ ₃ 3	□₄ 4	□ ₅ 5	🗖 e 🧕
15. Fatigue	D ° 0	□ ₁ 1	□ ₂ 2	□ ₃ 3	□ ₄ 4	□ ₅ 5	🗖 e 👲
16. Feeling "slowed down"	D ° 0	□ ₁ 1	□ ₂ 2	□ ₃ 3	□₄ 4	□ ₅ 5	🗖 e 🧕
17. Feeling like "in a fog"	D ° 0	□ ₁ 1	□ ₂ 2	□ ₃ 3	□₄ 4	□ ₅ 5	🗖 e 👲
18. Difficulty concentrating	D 0 0	□ ₁ 1	D 2 2	□ ₃ 3	4 4	□ ₅ 5	□ ₀ 6

## 13.2 APPENDIX 2: Physical and Cognitive Activity Assessments

Please indicate your level of cognitive activity in the past day [insert date]:

1.	Cognitive Activity:	$\square_0$ Complete cognitive rest
		I Not attending school/work, but doing light cognitive activity, (e.g. watching TV, pleasure reading or using the Internet)
		□ 2 Not attending school/work, but doing moderate cognitive activity, (e.g. homework, academic reading, school/work-related computer use)
		□ 3 Attending school/work with decreased workload (e.g. not taking exams, taking a reduced number of courses)
		Full unrestricted participation in school/work including all exams, assignments, and homework

Please indicate your level of physical activity in the past day [insert date]:

2.	Physical Activity:	$\square_0$ Complete physical rest			
		$\Box_1$ Light aerobic activity (e.g. walking, swimming or stationary cycling)			
		$\square_2$ Moderate non-contact exercise (e.g. running, skating drills in hockey, running drills in soccer or football)			
shooting drills in sports, partial participation in gy classes) $\Box_4$ Complex activity or drills with full participati		$\square_3$ Complex activity or drills involving partial participation (e.g. passing or shooting drills in sports, partial participation in gym class or exercise classes)			
		$\Box_4$ Complex activity or drills with full participation (e.g. full contact practice, normal training activities, full participation in gym class or exercise classes)			
		$\square_5$ Normal activity level without limitation, including normal game or scrimmage play			

#### 13.3 APPENDIX 3: Sleep Assessment

1. How many naps did you take yesterday? [insert date]?  $\Box_0$  None  $\Box_2$  Two  $\Box_4$  Four  $\Box_1$  One  $\Box_3$  Three  $\Box_5$  Five

For each nap that you took, please record the approximate start time and duration. If you did not take a nap, please continue to Question 2.

	Approximate Start Time		start Time	Duration of Nap		
	a. 1 st Nap	:	$\square_1$ a.m. $\square_2$ p.m.	$\_\1$ minutes $\square_2$ hours		
	b. 2 nd Nap	:	$\square_1$ a.m. $\square_2$ p.m.	$\_\_$ $\square_1$ minutes $\square_2$ hours		
	c. 3 rd Nap	:	$\square_1$ a.m. $\square_2$ p.m.	$\_\1$ minutes $\square_2$ hours		
	d. 4 th Nap	:	$\square_1$ a.m. $\square_2$ p.m.	□_1 minutes □_2 hours		
	e. 5 th Nap	:	$\square_1$ a.m. $\square_2$ p.m.	$\_\_$ $\_\_$ $\square_1$ minutes $\square_2$ hours		
2.	What time did you go to bed yesterday?	:	$\square_2$ p.m. $\square_1$ a.m.			
3.	How long did it take you to fall sleep?		$\square_1$ minutes $\square_2$ hours			
4.	How many times did you wake during the night?	
 
□0 Never
 
□1 1-2 times
 
□2 3-4 times
 
□3 more than 4 times
 
	nes			
5.	What time did you get up today?	:	$\square_1$ a.m. $\square_2$ p.m.			
6.	About how many hours did you sleep last night?	hours				

7. Please comment on any unusual activities yesterday (insert date): (i.e. sickness, holiday, daylight savings time, travel, etc.)

